### 4.2 Exclusion Criteria

- Cardiopulmonary resuscitation less than 7 days ago.
- Cardiogenic shock, ST-elevation myocardial infarction, or other clinical conditions that require immediate ICU admission or urgent PTCA.
- Systolic blood pressure lower than 100 mm Hg at presentation.
- Primary rhythmogenic cause of acute decompensation (ventricular tachycardia, reentry tachycardia, atrial fibrillation or atrial flutter with a ventricular rate exceeding 140 beats per minute).
- Non-ST-elevation myocardial infarction as primary diagnosis.
- Severe aortic or mitral stenosis.
- Adult congenital heart disease as primary cause of acute HF.
- Hypertrophic obstructive cardiomyopathy.
- Isolated right ventricular failure due to pulmonary hypertension.
- Chronic kidney disease with creatinine levels  $> 250$   $\mu$ mol/l.
- Bilateral renal artery stenosis.
- Severe sepsis or other causes of high output failure.
- Liver Cirrhosis Child-Pugh class C.
- Systemic Lupus erythematosus and related diseases.
- Acute aortic dissection.

- Porphyria.
- Previous adverse reactions to nitrates.
- Known hypersensitivity to hydralazine or dihydralazine.
- Patient in an emergency situation resulting in an inability to give informed consent.

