## Study Therapy Early Goal-Directed Group

Early goal-directed preload and afterload decrement with a target systolic blood pressure of 90 mm Hg to 110 mm Hg for the entire hospitalization. This blood pressure target is considered to represent the maximal feasible afterload decrement without impairment of critical organ perfusion (40). This pathophysiologic goal is pursued by predominately applying nitrates, ACE-inhibitors and ARBs at maximal tolerable (avoiding arterial hypovolemia and inadequate arterial perfusion pressure) doses.

The treatment schedule is displayed in Figure 5a. Accordingly, on day 1 (0 h till 24 h) treatment will be started with one capsule of sublingual nitrates (containing usually 0.8 mg glyceryl trinitrate) or two applications of nitrospray (containing usually 0.4 mg

glyceryl trinitrate per application) in combination with transdermal nitrates (for example Nitroderm TTS® 10 mg / 24h) in a dosage between 40 to 80 mg / 24 h depending on admission systolic blood pressure. 10 and 20 minutes after the initial sublingual nitrates capsule or nitrospray application, one additional capsule of sublingual nitrates (containing usually 0.8 mg glyceryl trinitrate) or two applications of nitrospray (containing usually 0.4 mg glyceryl trinitrate per application) will be administered (in total three capsules sublingual nitrates or six applications of nitrospray). After 6 hours a dose adjustment of the transdermal nitrates dependent on systolic blood pressure will be performed (Figure 5a). On day 1 and 2, transdermal nitrates will be applied as continuous therapy for 24 hours each patch. In patients without severe renal dysfunction (defined as calculated glomerular filtration rate below 30 ml/min) and without evidence of an acute coronary syndrome (accompanying chest pain, new ECG changes, elevated cardiac Troponin T), hydralazine will be added orally to achieve an early maximal vasodilative effect and to avoid tolerance to nitrates. Hydralazine will be administered in a fix dosage of 25 mg every 6 hours (1 - 1 - 1 - 1) for the first 48 hours after study inclusion. Patients with evidence for an acute coronary syndrome (Cave: “coronary steal”) or with severe renal dysfunction (Cave: accumulation) will not receive hydralazine, but nitrates only.

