Transthoracic echocardiography (TTE) for the detailed assessment of systolic, diastolic, and valvular function will be performed as clinically indicated in the majority of patients. Response to therapy will be documented by daily clinical patient assessment using a predefined questionnaire as well as a visual analogue scale to record subjective course of dyspnea. Periodical measurements of electrolytes (sodium, potassium) and creatinine at study inclusion, every 24 to 72 hours during the first week and at discharge will be accomplished.

In the further course of treatment (usually one or two days before discharge), a beta-blocker will be added to this therapy at very low dose. Augmentation of the beta-blocker dosage will only be performed after discharge during the outpatient phase. Spironolactone (an aldosteron-receptor-antagonist) may be added in patients who remain in NYHA classes III and IV and in patients with low potassium concentration at presentation, as long as they have a serum creatinine below 150 µmol/l.

Despite early blood pressure intervention in the study group, special attention will be given to the final drug-treatment in both study groups. As ACE-inhibitors / ARB and beta-blockers provide the best documented survival benefit in patients with HF (3,7), initiation of a beta-blocker before hospital discharge will be strongly endorsed, and treatment of an equal percentage of patients in both arms with these two agents remains crucial.

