## **6. Risks and Benefits**

Early goal-directed preload and afterload decrement by aggressive vasodilatation with a target systolic blood pressure of 90 mm Hg to 110 mm Hg by using a fix therapy schedule has the potential to achieve faster cardiac re-compensation without jeopardizing major organ blood supply. Therapy with nitrates in dosages known to decrease preload and afterload in acute HF has been tested in two clinical trials and found to be superior to low dose nitrates in patients treated in mobile ICU. However,

the main potential adverse event induced by aggressive vasodilatation is arterial hypotension and consecutive decrement in renal and other major organ blood flow. Data from the A-HeFT study assure that the risk for an aggravation of a preexisting arterial hypotension (systolic blood pressure below 110 mm Hg) in therapy with nitrates and hydralazine is low, and that also patients with preexisting arterial hypotension will benefit from this therapy option (44). It is the concept of this study that the clinical hemodynamic monitoring available in the emergency department (first 24 hours) and general medical ward (second 24 hours and remaining hospitalization) allows the judicious use of this fix therapy schedule to achieve requested vasodilatation and the target blood pressure. It is important to note that in case of symptomatic arterial hypotension easy applicable measures to increase blood pressure are available. A major advantage of the transdermal application form of nitrates during the initial part of the study is the option to stop drug resorption by removing the patch.

During the first 48 hours patients would be encouraged to perform gymnastics of their calves before standing up and leave their beds only in company of the responsible nurse, in order to avoid symptoms of orthostatic hypotension. In case of headache, which is a common side effect in nitrate therapy, treatment would be effectuated with paracetamol (e. g. Perfalgan®) 1 g intravenous.

In order to avoid a possible “steal phenomenon” of hydralazine, patients with evidence for an acute coronary syndrome will be treated only with nitrates and will not receive hydralazine.

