### b. Secondary objectives

Secondary endpoints are:

- All-cause mortality at 180 days.
- HF re-hospitalization at 180 days.
- Death or re-hospitalization from all causes at 180 days.
- Need for ICU admission during initial hospitalization.
- Acute coronary syndrome during initial hospitalization.
- Symptomatic hypotension during initial hospitalization.
- B-type natriuretic peptide (BNP) and creatinine level at 48 h and at discharge.
- Changes in circumferences of both legs and central venous pressure during hospitalization.
- Change in patient-assessed dyspnea at 48 h and prior to discharge.
- Blood pressure course over the first 6 days.
- Time to disappearance of a third heart sound (if present initially).
- Time to discharge.
- In-hospital days for HF at 180 days and 360 days.
- Total treatment cost at 180 days and 360 days.
- Functional status at 180 days and 360 days.
- Quality of life (EQ-5D-3L) at 180 days and 360 days.
- Fractures due to falls within 180 days and 360 days.
- Death or HF re-hospitalization at 360 days.

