### **j. Data validation**

The following data validation checks will be performed:

1. For critical items, univariate, multivariate and cross-module checks will be performed. This will include valid-value (e.g. selections of only “yes” or only “no”), valid-range (e.g. range of vital signs), and missing-value (e.g. age).
2. Occurrence of events or items containing dates, will be checked whether they occurred on/after the date of randomization with the only exception being items from the medical history (e.g. date of previous stroke, previous echocardiogram) which could have occurred before the randomization.

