Edema – no. (%)	xx (xx%)	xx (xx%)	xx (xx%)
Ascites – no. (%)	xx (xx%)	xx (xx%)	xx (xx%)
Pulmonary attenuation – no. (%)	xx (xx%)	xx (xx%)	xx (xx%)
Pulmonary wheezing – no. (%)	xx (xx%)	xx (xx%)	xx (xx%)
Pulmonary Rales – no. (%)	xx (xx%)	xx (xx%)	xx (xx%)
Vital parameters:			
Diastolic blood pressure –mmHg (±SD)	xx±xx	xx±xx	xx±xx
Systolic blood pressure -mmHg (±SD)	xx±xx	xx±xx	xx±xx
Heart frequency – bpm (±SD)	xx±xx	xx±xx	xx±xx
Breathing frequency – rpm (±SD)	xx±xx	xx±xx	xx±xx
Oxygen saturation – % (±SD)	xx±xx	xx±xx	xx±xx
Temperature – °C (±SD)	xx±xx	xx±xx	xx±xx
Trigger of the current AHF episode			
Dietary and medication related causes			
Dietary indiscretion – no. (%)	xx (xx%)	xx (xx%)	xx (xx%)
Volume overload – no. (%)	xx (xx%)	xx (xx%)	xx (xx%)
Alcohol – no. (%)	xx (xx%)	xx (xx%)	xx (xx%)
Non-compliance to medication – no. (%)	xx (xx%)	xx (xx%)	xx (xx%)
Medication (NSAID, changes of diuretics) – no. (%)	xx (xx%)	xx (xx%)	xx (xx%)
Cardiac causes			
Myocardial ischemia / necrosis – no. (%)	xx (xx%)	xx (xx%)	xx (xx%)
Myocarditis – no. (%)	xx (xx%)	xx (xx%)	xx (xx%)
Uncontrolled hypertension – no. (%)	xx (xx%)	xx (xx%)	xx (xx%)
Arrhythmia (Afib, VT, bradycardia, AV-Block) – no. (%)	xx (xx%)	xx (xx%)	xx (xx%)
Progressive valvular disease (MI, AS) – no. (%)	xx (xx%)	xx (xx%)	xx (xx%)
Non-cardiac causes			
Pulmonary disease (PE, COPD) – no. (%)	xx (xx%)	xx (xx%)	xx (xx%)
Thyroid disorders – no. (%)	xx (xx%)	xx (xx%)	xx (xx%)
Physical, emotional, environmental stress – no. (%)	xx (xx%)	xx (xx%)	xx (xx%)
Infection – no. (%)	xx (xx%)	xx (xx%)	xx (xx%)
Anemia (<100g/l) – no. (%)	xx (xx%)	xx (xx%)	xx (xx%)
Unknown – no. (%)	xx (xx%)	xx (xx%)	xx (xx%)

Data are presented as absolute number and percentages (%) or means  $\pm$  standard deviations SD or median (25% to 75% interquartile range IQR) or median.

BMI= body mass index, CAD= coronary artery disease, PCI= percutaneous coronary intervention, ICD= implantable cardioverter-defibrillator, CRT= cardiac resynchronization therapy, COPD= chronic obstructive pulmonary disease, HJR= hepatjugular reflux, AHF= acute heart failure, NSAID= Nonsteroidal anti-inflammatory drugs, Afib= atrial fibrillation, VT= ventricular tachycardia, AV Block= atrial ventricular block, MI= mitral insufficiency, AS= aortic stenosis, PE= pulmonary embolism

Table 1 Baseline Clinical Characteristics and Medical History

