#### i. Brief summary of adverse events

The following AEs will be collected:

- Headaches
- Dizziness
- Fall
- Creatinine increase > 30% of baseline
- Hypokalemia < 3.5 mmol/l
- Hyperkalemia > 5 mmol/l
- Arrhythmia requiring therapy
- Systolic arterial hypotension < 80 mm Hg over 30 minutes
- Acute coronary syndrome
- Transfer to the intensive care unit
- Cardiopulmonary resuscitation

The following SAEs will be collected

- In-patient hospitalization
- Prolongation of existing hospitalization
- Life threatening event
- Death

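### ACS, arrhythmia and potassium events have no new-or-worsened criterion, so conditions present at entry may be counted as in-hospital harms and dilute the comparison

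*Combined protocol and SAP*

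**What the plan says.** **What is counted.** SAP 2.2 (Secondary objectives) lists "Acute coronary syndrome during initial hospitalization", with no definition beyond the stay. SAP 11.1.1 lists ACS, arrhythmia requiring therapy, potassium below 3.5 mmol/l and "Hyperkalemia > 5 mmol/l". These are absolute limits or bare labels. Creatinine, in the same list, is an increase of more than 30% over baseline. SAP 11.1.3 compares total events per patient between arms by chi-square, with no reference to baseline status. For the safety population it sets an end to counting (last confirmed intake) but no start.

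**Who can enter.** Protocol 4.2 excludes ST-elevation infarction, but other infarction only in the form "Non-ST-elevation myocardial infarction as primary diagnosis". The early goal-directed therapy section adds hydralazine in patients without severe renal dysfunction and "without evidence of an acute coronary syndrome (accompanying chest pain, new ECG changes, elevated cardiac Troponin T"). Protocol 6 says that "patients with evidence for an acute coronary syndrome will be treated only with nitrates and will not receive hydralazine". SAP Table 1 has baseline trigger rows for "Myocardial ischemia / necrosis" and for arrhythmia. Protocol 4.2 excludes only a primary rhythmogenic cause of the decompensation and has no potassium criterion. Protocol 5 (General Procedure) mentions spironolactone "in patients with low potassium concentration at presentation". The control-group section names hyperkalaemia on admission as a reason to reduce or stop an ACE-inhibitor or ARB.

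**What guards against entry cases.** SAP 4.2 (Data validation) says that dated events "will be checked whether they occurred on/after the date of randomization", medical history excepted. Protocol 10.6.1 defines an adverse event in general temporal terms, in a patient who has been given a product.

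**The concern.** A condition present before treatment starts cannot have been caused by it. If such conditions are counted equally in both arms, they raise both rates, shrink the risk difference and move the risk ratio toward 1. For harm endpoints that is the unsafe direction, because a real increase looks smaller. Safety is part of the stated objective, and ACS and potassium are natural things to watch under rapid vasodilatation with ACE-inhibitor or ARB up-titration. The plan already applies the principle to creatinine and leaves it out for the items beside it.

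**Working it through.** **Step 1: does the date check close the gap?** It works by calendar date.

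| Entry condition | Result of the check |
|---|---|
| Event dated before the day of randomisation | Removed |
| ACS evidence or abnormal potassium dated the same day, before treatment | Passes |
| Arrhythmia or abnormal potassium still present on day 2 | Passes |

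Patients are enrolled in the emergency department, so same-day findings are likely. Potassium is measured at inclusion, every 24 to 72 hours in the first week and at discharge (protocol 5). A value already out of range therefore has several later chances to be recorded.

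**Step 2: dilution in general.** The plan gives no event rate or entry prevalence for these items, so there is no figure to reproduce. Let q be the entry prevalence (equal in both arms) and p the risk of a new event.

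Counted risk = q + (1 − q) × p. The risk difference shrinks by the factor (1 − q).

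Illustration with assumed rates, using ACS or arrhythmia as the example: p = 5% control and 10% intervention, 385 per arm (protocol 8.3), two-sided 5%, normal approximation. At q = 10%:
- control 0.10 + 0.90 × 0.05 = 0.145
- intervention 0.10 + 0.90 × 0.10 = 0.190
- risk ratio 0.190 / 0.145 = 1.31, against 2.00 for new events only

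| Entry prevalence q | Risk ratio, all counted | Power, all counted | Power, entry cases left out (risk ratio 2.00) |
|---|---|---|---|
| 0% | 2.00 | 75% | 75% |
| 5% | 1.49 | 52% | 73% |
| 10% | 1.31 | 39% | 71% |
| 20% | 1.17 | 24% | 65% |

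The table shows the direction and how it depends on q. It does not estimate what happens in this trial.

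**Step 3: potassium above 5 mmol/l.** All inputs are assumed: mean 4.2 or 4.3 mmol/l, between-patient SD 0.45 or 0.6, within-patient SD 0.2 or 0.3, one inclusion value, four later values, and a shift of 0.2 mmol/l in the intervention arm. There were 400,000 simulated patients per setting. As written, a patient counts if any later value exceeds 5. With the baseline rule, only patients with inclusion potassium from 3.5 to 5 are in the risk set. Power is for 385 randomised per arm. The new-crossing analysis uses the in-range subset, about 283 to 335 per arm.

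| Mean / between SD / within SD | As written: control, intervention | Risk ratio (power) | New crossings: control, intervention | Risk ratio (power) |
|---|---|---|---|---|
| 4.2 / 0.45 / 0.2 | 10.3%, 20.2% | 1.97 (97%) | 7.0%, 17.4% | 2.50 (99%) |
| 4.2 / 0.6 / 0.3 | 22.1%, 32.3% | 1.46 (89%) | 16.5%, 29.0% | 1.76 (95%) |
| 4.3 / 0.45 / 0.2 | 14.7%, 26.6% | 1.81 (98%) | 9.3%, 22.0% | 2.35 (above 99%) |
| 4.3 / 0.6 / 0.3 | 26.8%, 38.0% | 1.42 (91%) | 19.1%, 32.6% | 1.70 (96%) |

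The other four combinations give risk ratios between these extremes. Over all eight, the risk ratio is about 1.4 to 2.0 as written and 1.7 to 2.5 for new crossings. Power is about 89% to 99% as written and at least 95% for new crossings. With no treatment effect, 10% to 27% of patients are flagged, and 31% to 58% of those were already above 5 at inclusion.

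**The case against.** **The plan does not say that entry conditions are counted.** A reader might infer that it does. The adverse-event definition refers to a patient who has been given a product. Triggers are recorded separately as baseline data. The assessment schedule in SAP 3.5 shows the active adverse-event search starting on day 2, if the extracted columns are right. This stands as far as it goes: the text neither includes nor excludes entry cases, so the supportable wording is that they may be counted. It does not close the gap, because a condition that persists to day 2 meets every stated criterion.

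**A false ACS signal is not shown.** A reader might infer one, because only the intervention arm needs an ACS judgement for the hydralazine decision in an open-label trial. But the exclusion criteria make ACS a question for every patient before randomisation, ECG is part of the diagnosis in all, samples for Troponin T are taken in both groups, and the adverse-event search covers both arms. Nothing in the documents supports unequal recording. With equal recording, randomisation balances entry cases in expectation, and the result is attenuation only.

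**A larger potassium gain needs a different rule.** Risk ratios of 2.1 to 4.6 appear only if a rise of at least 0.5 mmol/l is also required. The fix below does not require that.

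**The consequences are limited.** SAP 6.6.4 makes secondary analyses explorative, with p-values not read against a threshold, so power is only a rough yardstick here. The adverse-event table is supplementary and produced if requested. An absolute potassium limit is also a legitimate safety measure. All of this stands. It lowers the weight of the point and is a reason to keep the all-cases count, but it does not justify leaving entry status out.

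**Conclusion.** The gap is real and minor. ACS, arrhythmia and potassium events lack the baseline reference that creatinine has, patients can be enrolled with these conditions, and the calendar-date check does not remove same-day or persisting cases. Counting them would attenuate the harm comparison.

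The amount cannot be determined from the documents. The figures above rest on assumed prevalences, incidences and potassium distributions, and on equal recording in both arms. For potassium, the effect on the risk ratio is visible but the gain in power is modest. For ACS and arrhythmia, the dilution depends wholly on an unknown entry prevalence. The primary endpoint is not touched.

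**What to change.** - **SAP 11.1.1, potassium:** report hypo- and hyperkalaemia as new crossings among patients whose inclusion potassium was in range. Add a table by baseline category, so that worsening of an already abnormal value stays visible. Inclusion potassium is taken before study treatment should act, so restricting on it keeps the randomised comparison.
- **SAP 2.2 and 11.1.1, ACS and arrhythmia:** count an event only if it is new or worsened after randomisation. Use the recorded admission trigger and the baseline troponin to identify entry cases, and show entry status by arm.
- **All-cases count:** keep it as a supplementary line.

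The cost is SAP wording, a little more derivation and fewer counted events. Inclusion potassium, the trigger and baseline samples for troponin are already planned. An onset rule by clock time should not be assumed feasible, because the data checks mention only dates. No clinical rule changes.
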